5.1.7 Histological Evaluation

Esophageal biopsy samples will be evaluated to confirm eligibility. Biopsy samples will be stained with hematoxylin and eosin stain. Intraepithelial eosinophils will be counted in all HPFs using 400X light microscopy. A HPF will be counted only if at least half of the field is occupied by tissue. The maximum eosinophil count per HPF will be reported for each esophageal biopsy site (at each

of 2 levels) with a minimum of 2 biopsies at each level. In addition to the evaluation for eosinophilia, all biopsy samples will be assessed for other histologic changes including epithelial hyperplasia, intercellular edema, and fibrosis.

Specimens will be examined with respect to the maximum eosinophil counts and other histologic changes. Together with the EoE Clinical Symptom Score, the maximum eosinophil count per HPF for each specimen (from the total of all specimens) will be used to determine response to treatment.

The maximum eosinophil count will be defined as the highest number of eosinophils observed in any single HPF from an esophageal specimen. All specimens from all esophageal sites will be considered in determining the resolution of eosinophilia. A maximum eosinophil count will be recorded for the esophagus. The highest peak counts at a given timepoint will be referred to as the maximum eosinophil count for that timepoint.

5.1.8 Endoflip

Esophageal distensibility utilizing the endolumenal functional lumen imaging probe (EndoFLIP, Medtronic, USA) will be performed with measurements taken as part of the esophagogastroduodenoscopy procedure. The EndoFLIP procedure must be performed before biopsies are collected. Procedural order should be: EREFS/imaging, EndoFLIP, then biopsies. The EndoFLIP device is a catheter-based procedure that measures the cross-sectional area at multiple sites along the esophagus with simultaneous intraluminal pressure recordings during volumetric distension of the esophagus. The analyses of cross-sectional area versus pressure relationships of the esophagus allow for determination of esophageal compliance as well as the distensibility plateau. The distensibility plateau has been shown to be significantly reduced in adult patients with EoE compared to healthy controls²⁹. Moreover, the esophageal distensibility has been associated with outcomes of both food impaction and need for esophageal dilation²⁵. Endoflip has also been shown to correlate with symptoms in pediatric cohorts.³⁰

Endoflip are standard of care at the time of endoscopy to measure esophageal function.

Esophageal epithelial integrity is affected by the presence of dilated intercellular spaces (DIS), or spongiosis (intercellular edema), which affects paracellular permeability of the esophageal lumen. DIS is an important histologic feature in GERD and EoE which inversely correlates with MI measurements (i.e., lower impedance values with increasing DIS).

Patients with EoE have shown to decreased impedance compared to GERD or achalasia.³¹ Esophageal impedance will be measured by MiVu.

5.1.9 Diet Diary

Subjects will indicate the duration and amount of food taken on a daily basis during the food reintroduction period.

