3.1.2 Food Introduction

If research subjects have a clinical response to dupilumab, they will introduce an EoE trigger food at one serving size per day. After 12 weeks, repeat EGD and symptoms score will be obtained. 12 weeks is being used as determined clinical and histologic responses can be seen at that time point in previous clinical studies¹⁸.

The foods (milk, egg, soy, and wheat) to be introduced after having caused exacerbation of their EoE by standard definitions:

- Addition of a single food lead to exacerbation of esophageal eosinophilia (increase of greater than 15 eos/hpf) or
- Removal of a single food lead to normalization of biopsy (esophageal eosinophilia showed less than 6 eos/hpf)
- AND
- History of either milk, egg, soy, or wheat induced EoE based on introduction of the food and symptoms in the last 12 months

Foods in phase 1 will be introduced as one serving size at week 13. If biopsy at week 25 are less than 6 eosinophils/HPF, the subjects will have one of 2 options

- Increase the serving size to 2 servings a day or
- Add an additional EoE trigger food

If the week 25 biopsy show 6-15 eosinophils/hpf, the diet will remain the same

If the week 25 biopsy show >15 eosinophils, the diet will decrease to ½ serving size a day

For the week 38 endoscopy with biopsy, the three scenarios are

If the biopsy show < 6 eosinophils/hpf, the three options are

- Increase the serving size to ad lib (if one food) or
- Add a 3rd EoE trigger food or
- Increase the serving size of 1st and 2nd foods to 2 serving size a day

If the biopsy shows 6-15 eosinophils/hpf, the plan is to remain at the current diet

If the biopsy show >15 eosinophils/hpf, the plan is to decrease the serving size by 50%

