4.2 Phase 2: Food Introduction

4.2.1 Visit 5, 9, 13

1 week (+/- 3 days) after visit 4, 8 and 12

- EoE Symptom Score-PEESS and PESQ (SOC procedure)
- Drug disposition
- New food introduction
- Monitor drug compliance
- AE assessment
- Physical Examination including vital signs with height and weight

4.2.2 Visit 6, 10, 14

2 weeks (+/- 4 days) after preceding visit. This visit can be done by remote research visit.

- EoE Symptom Score-PEESS and PESQ (SOC procedure)
- Drug disposition
- Review food diary
- Monitor drug compliance
- AE assessment
- Physical Examination including vital signs with height and weight

4.2.3 Visit 7, 11, 15

5 weeks (+/- 4 days) after preceding visit. This visit can be done by remote research visit.

- EoE Symptom Score-PEESS and PESQ (SOC procedure)
- Review food diary
- Monitor drug compliance
- AE assessment

4.2.4 Visit 8, 12, 16

- Upper Endoscopy with biopsy-4 esophageal biopsies (SOC procedure)
- EoE Symptom Score-PEESS and PESQ
- EoE QOL
- Review food diary
- Drug disposition (except for visit 16)
- Monitor drug compliance

- AE assessment
- Physical Examination including vital signs with height and weight
- Endoflip and/or esophageal impedance
- Research bloods: (T cell phenotype, PBMC RNAseq, peripheral blood eosinophils and progenitors, proteomics)-15 ml of blood
- Research Biopsies: Esophageal biopsy RNAseq-6 esophageal biopsies
- AE assessment

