5.3.2 Secondary Endpoints

Secondary endpoints will include the following:

- Maintenance of resolution (<15 eosinophils/HPF on peak measurements) of eosinophilia observed on esophageal biopsies
- Maintenance of remission (<6 eosinophils/HPF on peak measurements)
- Change in mean esophageal eosinophil count from baseline to the end of treatment.
- Change in symptoms scores at the end of treatment compared to baseline
- Interval change on a validated endoscopic scoring system, EREFS
- Interval change on esophageal compliance and distensibility measured by EndoFlip
- Interval change in mRNA transcriptome profile (esophageal tissue), Th2 phenotype (peripheral blood), blood eosinophilia
- Change in the Eosinophilic Esophagitis Quality of Life Score from baseline to the end of treatment

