5.4 Statistical Methods

5.4.1 Analysis Populations

An Intent to Treat population (ITTP) will be used as the primary analysis population. This will include all patients that were enrolled in the study.

A Per Protocol population (PPP) will be used as a sensitivity analysis population. This will include all patients that did not have a major protocol violation.

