6.1.3 Treatment Compliance and Adherence

It is the Investigators' responsibility to ensure that subjects are correctly instructed on how to take their study medication. Records of study medication used and intervals between visits will be kept during the study. Subjects will be asked to return their unused medication (box(es)) when they come back for their study visits. All unused medication (boxes) should be returned at each study visit and the end of the study. The study drug will be dispensed by the Investigator, or by a qualified individual under the Investigator's supervision.

At each visit, prior to dispensing trial medication, previously dispensed trial medication will be retrieved by the Investigator and compliance assessed. A compliance of > 80% over the treatment period is sought. Subjects exhibiting poor compliance as assessed by counts and response to the question "Did you take your dupilumab regularly?" will be counseled on the importance of good compliance to the study dosing regimen.

Non-compliance is defined as taking less than 80% of trial medication during any evaluation period (visit to visit). Subjects who are persistently non-compliant may be withdrawn from the study.

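### The two histologic maintenance endpoints count a subject as maintained on biopsy alone, whether or not the trigger food was eaten

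*Combined protocol and SAP*

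**What the plan says.** - **Exposure.** Section 3.1 has each subject eat one daily serving of a known trigger food for 12 weeks, followed by endoscopy. The synopsis objective is that dupilumab lets trigger foods back in without a histologic or symptomatic flare.
- **Diary.** Section 5.1.9: "Subjects will indicate the duration and amount of food taken on a daily basis during the food reintroduction period". Section 4.2 lists "Review food diary" at visits 6–8, 10–12 and 14–16. It attaches no minimum intake and no consequence to that review.
- **Maintenance endpoints.** Section 5.3.2 lists "Maintenance of resolution (<15 eosinophils/HPF on peak measurements) of eosinophilia observed on esophageal biopsies" and "Maintenance of remission (<6 eosinophils/HPF on peak measurements". Neither carries a condition on food eaten.
- **Compliance.** Section 6.1.3: "Non-compliance is defined as taking less than 80% of trial medication during any evaluation period (visit to visit". No equivalent exists for the food.
- **Analysis sets.** Section 5.4.1 takes all enrolled patients as the primary population. Of the per-protocol set, used as a sensitivity population, it says "This will include all patients that did not have a major protocol violation". That term is not defined.
- **Models and tests.** Sections 5.4.3.1 to 5.4.3.5 describe paired tests, a GEE model whose only stated explanatory variable is time point, and possible transformations. Recorded intake does not appear.

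**The concern.** A biopsy says something about tolerance of a food only if the food was eaten. Take a subject who has every injection, eats the food a handful of times and has a peak count of 2 eos/HPF at week 25. Under 5.3.2 that subject is maintained on both definitions, and nothing in the analysis plan separates them from someone who ate a serving every day.

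In most trials poor adherence dilutes the effect the sponsor hopes to show. Here the hoped-for finding is the absence of a flare, so uneaten food moves the maintenance rates toward it. The all-enrolled analysis is therefore not the cautious choice on this point. The per-protocol set, which would be the natural safeguard, does not say how food intake is treated. Some avoidance is plausible, because the inclusion criteria require symptoms on introducing the food within the last 12 months. What is at stake is a reported tolerance rate that includes people who were never really challenged.

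**Working it through.** **Inputs from section 5.6:** 30 enrolled, 64% expected to respond, 19 evaluable; alpha 0.05, power 80%, n = 20, detectable difference 11 eos/HPF, effect size 0.7. The implied SD of the change is 11/0.7 = 15.7. Sidedness is not stated; two-sided is assumed.

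**The plan's own figure.** 30 × 0.64 = 19.2, so 19 evaluable is right. A paired t-test (noncentral t) with effect size 0.7 needs n = 19 for at least 80% power. Power is 82% at n = 19 and 84% at n = 20. The stated sample size reproduces within one subject, so this point does not rest on a sample-size error. The evaluable count allows for drug non-response only, not for food non-adherence.

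**Assumptions, because the documents give no food-adherence rate:** f = share who do not eat the food; p = true maintenance rate among eaters; q = share of non-eaters who stay in remission.

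**Maintenance rate.** Observed rate = (1 − f)p + fq. With q = 1:

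| f | p = 30% | p = 50% | p = 70% |
|---|---|---|---|
| 10% | 37% | 55% | 73% |
| 20% | 44% | 60% | 76% |
| 30% | 51% | 65% | 79% |
| 50% | 65% | 75% | 85% |

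For f = 20%, p = 50%: 0.8 × 0.50 + 0.2 × 1 = 0.60. If only 90% of non-eaters stay in remission, the f = 20% row becomes 42%, 58% and 74%. In people, 20% of 19 is 3.8, and a 10-point shift is 1.9.

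**Effect of how low-intake subjects are handled** (f = 20%, p = 50%, q = 1):
- counted as maintained, as 5.3.2 now reads: 60%;
- removed from the denominator: 50%;
- counted as not maintained: 0.8 × 0.50 = 40%.

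If those subjects avoided the food because they could not tolerate it, 40% is the honest figure, and simply dropping them overstates tolerance by 10 points.

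**Primary endpoint, if the pair is pre-food versus post-food.** Let eaters have mean change 11 and SD 15.7, and non-eaters mean change 0 and the same SD. Mean = (1 − f) × 11; SD = √(15.7² + f(1 − f) × 11²). Power at n = 19:

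| f | mean rise | SD | power |
|---|---|---|---|
| 0 | 11.0 | 15.7 | 82% |
| 10% | 9.9 | 16.1 | 72% |
| 20% | 8.8 | 16.3 | 60% |
| 30% | 7.7 | 16.5 | 49% |
| 50% | 5.5 | 16.7 | 28% |

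**Primary endpoint, if the pair is week 25 versus week 38.** Both endoscopies then follow the start of food. A subject who skips the food in the first interval and eats it in the second enlarges the change; the reverse pattern shrinks it. The direction is not fixed. Section 3.1 calls the week 25 procedure the second endoscopy, which favours the pre/post reading, but the wording in 5.3.1 allows either.

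**The case against.** The strongest case on the other side is that intake does not go unobserved. The diary is reviewed three times in each food period. Section 3.4.4 allows withdrawal for not complying with protocol requirements, and section 4.6 lets the investigator withdraw subjects who violate the study plan. Not eating the assigned food could well be ruled a major protocol violation. Section 1.5 says families strongly want a wider diet, so intake may be good. The study is an open-label exploratory pilot, and section 5.5 makes the maintenance endpoints exploratory. At n = 19 the sampling error around 50% is 1.96 × √(0.25/19) = ±22 points, more than twice the illustrated 10-point bias.

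Most of this stands as mitigation. It does not close the gap: the withdrawal clauses are discretionary, none names a food criterion, and deciding who violated the plan after open-label biopsies are known is what a prespecified rule prevents. A wide interval also does not remove a bias that always points the same way.

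Four stronger readings are tempting and are not supported:

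- *Every endpoint is read from the biopsy alone.* Section 5.3.2 also lists symptom scores, EREFS, EndoFlip, quality of life and blood markers, and 5.1.7 uses the symptom score alongside the count to judge response. None measures intake, but the claim holds only for the two histologic maintenance endpoints.
- *A non-eater stays in the per-protocol set because they pass the drug rule.* Section 5.4.1 never ties that set to the 80% rule in 6.1.3. The defect is an undefined term.
- *The primary endpoint is biased toward success.* It is a test for a difference with no success margin, and its direction depends on the endoscopy pair.
- *The escalation rules in 3.1.2 are wrong.* They do turn on the count ("If biopsy at week 25 are less than 6 eosinophils/HPF, the subjects will have one of 2 options"; "If the biopsy show < 6 eosinophils/hpf, the three options are"), while 3.1 also reduces the food for increased symptoms. Diet progression is clinical management, and this point makes no claim about it.

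**Conclusion.** The point holds for the two histologic maintenance endpoints. As written, they count an unchallenged subject as a success, and the bias runs toward apparent tolerance provided non-eaters stay in remission more often than eaters. Its size cannot be derived from the documents. Under the assumed 10–30% non-eating with all non-eaters in remission, a true 50% reads as 55–65%. For the primary endpoint, uneaten food dilutes a pre-food to post-food change (a rise of 11 becomes 8.8 at 20% non-eating); on a week 25 versus week 38 reading no direction can be stated. The change should be made even in a pilot, because the maintenance rate is the figure most readers will take away and the data needed to qualify it are already collected.

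**What to change.** Before analysis:

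1. Define food exposure from the diary for each interval with a fixed assigned amount. An example is at least 80% of assigned daily servings between food start and that endoscopy. This borrows the level in 6.1.3; the sponsor should set and justify the threshold. For ad lib periods no assigned amount exists, so summarise the recorded amount instead.
2. In 5.4.1, define major protocol violation and name failure to meet the exposure criterion as one.
3. Keep the all-enrolled analysis as primary. Beside it, report the maintenance rates and the primary change in the food-exposed set as a supplementary analysis, with a summary of recorded intake.
4. Count subjects who stopped or cut the food because of symptoms as not maintained. Report low intake without recorded symptoms separately, and add a sensitivity analysis that counts those subjects as not maintained, so that hidden intolerance cannot inflate the rate.

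The cost is SAP wording and the use of data already being collected; dosing, diet rules and visits do not change. The downside is that the diary is self-reported and the exposed set may lose a few subjects from an already small sample.

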5.1.10 Pregnancy testing

A urine pregnancy test will be performed for female subjects who are physically capable of becoming pregnant.

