Visit Number	1	2	3	4	5	6*	7*	8	9	10*	11*	12	13	14*	15*	16	17
Study weeks	1	3	8	12	13	15	20	25	26	28	33	38	39	41	46	51	52
Informed Consent/Assent	X																
Review Inclusion/Exclusion Criteria	X																
Demographics/Medical History	X																
Physical Examination	X	X	X	X	X	X		X	X	X		X	X	X		X	X
Vital Signs: BP, HR, RR	X	X	X	X	X	X		X	X	X		X	X	X		X	
Height and Weight	X	X	X	X	X	X		X	X	X		X	X	X		X	
EGD and biopsy				X				X ^a				X ^a				X ^a	
EREFs				X				X ^b				X ^b				X ^b	
EoE Symptom Score	X	X	X	X	X ^b	X ^b	X ^b	X ^b	X ^b	X ^b	X ^b	X ^b	X ^b	X ^b	X ^b	X	
EoE QOL	X			X				X				X					X
Food Introduction [#]				X				X				X					
Pregnancy Test	X																
Prior/Concomitant Medications	X																
Research laboratory	X			X				X				X				X	
CBC (safety)	X			X				X				X				X	

T cell phenotype, PBMC RNAseq	X			X				X				X				X	
Dispense Study Drug	X	X	X	X	X	X		X	X	X		X	X	X			
Drug Compliance		X	X	X	X	X		X	X	X		X	X	X		X	
Adverse Event Assessment		X	X	X	X	X	X	X	X	X	X	X	X	X	X	X	X

ERFS-EoE Endoscopy Reference Score

EoE QOL-Eosinophilic Esophagitis Quality of Life measure

*Visits can be done via remote research visit

a-EGDs are standard of care biopsies for food introduction

b-SOC procedures

Food Introduction

Foods in phase 1 will be introduced as one serving size at week 13. If biopsy at week 25 are less than 6 eosinophils/HPF, the subjects will have one of 2 options

- Increase the serving size to 2 servings a day or
- Add an additional EoE trigger food

If the week 25 biopsy show 6-15 eosinophils/hpf, the diet will remain the same

If the week 25 biopsy show >15 eosinophils, the diet will decrease to ½ serving size a day

[figure not shown]
For the week 38 endoscopy with biopsy, the three scenarios are

If the biopsy show < 6 eosinophils/hpf, the three options are

- Increase the serving size to ad lib (if one food) or
- Add a 3rd EoE trigger food or
- Increase the serving size of 1st and 2nd foods to 2 serving size a day

If the biopsy shows 6-15 eosinophils/hpf, the plan is to remain at the current diet

If the biopsy show >15 eosinophils/hpf, the plan is to decrease the serving size by 50%

FIGURE 1: STUDY DIAGRAM

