 21. Female patients who are pregnant, breastfeeding, or planning to become pregnant or breastfeed during the study
 22. Women of children bearing potential (WOCBP) who are unwilling to practice highly effective contraception prior to the initial dose/start of the first treatment, during the study, and for at least 12 weeks after the last dose. This includes female patients who experience menarche during the study duration and who are unwilling to follow the precautions for WOCBP.
-

23. Chronic or acute infection requiring treatment with systemic antibiotic, antivirals, or antifungal within 2 weeks of baseline visits

a. Patients maybe rescreened after infection resolves

24. Participants with active or suspected parasitic infection are excluded.

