4.5 Concomitant Medication

All prior and concomitant medications used within 14 days prior to the screening visit and through the end of the study will be recorded. The dates of administration, dosage, and reason for use will be included.

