5.1.11 Pregnancy

If a subject becomes pregnant during the trial, they will immediately stop receiving dupilumab. They will not be followed as there are no published reports of adverse events from pregnancy, fetus and dupilumab.

If the subject becomes pregnant, we will enroll them in a pregnancy exposure registry for women who take DUPIXENT during pregnancy. The purpose of this registry is to collect information about the health of subject and her baby. The registry is <https://mothertobaby.org/ongoing-study/dupixent/>.

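### The only scheduled pregnancy test is at Visit 1, so the rule to stop dupilumab on pregnancy has no scheduled detection step over about 50 weeks of dosing

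*Combined protocol and SAP*

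**What the plan says.** - **The test.** Section 5.1.10: "A urine pregnancy test will be performed for female subjects who are physically capable of becoming pregnant". It gives neither visit nor frequency. The screening text in section 3.1 places a urine test after consent, and inclusion criterion 6 (section 3.4.2) makes a negative urine or serum result a condition of entry.
- **The schedule.** In Table 1 the row "Pregnancy Test" has one mark, at Visit 1 (week 1). The procedure lists in sections 4.1 to 4.3 do not mention the test. That includes Visit 1 itself (section 4.1.1), where the first dose is given. The early termination visit (section 4.6.1) repeats Visit 8, so it has no test either.
- **The action on pregnancy.** Section 5.1.11: "If a subject becomes pregnant during the trial, they will immediately stop receiving dupilumab". The subject is also to be enrolled in an exposure registry.
- **Prevention.** Exclusion criterion 22 (section 3.4.3) rules out any woman of childbearing potential if "unwilling to practice highly effective contraception prior to the initial dose/start of the first treatment, during the study, and for at least 12 weeks", with those weeks counted from the final injection. On girls who mature during the trial, the same criterion says: "This includes female patients who experience menarche during the study duration and who are unwilling to follow the precautions for WOCBP". Criterion 21 excludes those who are pregnant or plan pregnancy during the study.

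**The concern.** The stop rule and the registry enrolment can act only once a pregnancy is known. After Visit 1 nothing on the schedule would make it known. Detection would depend on the subject reporting it, or on an unplanned test prompted by an adverse event assessment, a physical examination or an unscheduled visit (section 4.4). Until then dosing would continue.

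The gap is plainest for girls who reach menarche on study. The age range is 6 to 25 years and criterion 22 expects such cases, yet a girl not capable of pregnancy at Visit 1 would not be tested then and has no later scheduled test.

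What is at stake is subject safety and the working of the protocol's own rule. The primary and secondary efficacy analyses are not touched.

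**Working it through.** **Does one mark in Table 1 mean once only?** Not necessarily. Concomitant medications are also marked only at Visit 1, but section 4.5 extends them: "All prior and concomitant medications used within 14 days prior to the screening visit and through the end of the study will be recorded". No section does the same for the pregnancy test. Every other mention (sections 3.1, 3.4.2 and 5.1.10) either ties it to entry or gives no time. As written, there is one scheduled test.

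**Inputs.** From Table 1, Visits 1, 4, 8, 12 and 16 fall at weeks 1, 12, 25, 38 and 51. Section 3.3.1 gives 51 weeks of treatment. Section 6.1.2 gives weekly dosing to subjects aged 12 or over and above 40 kg, and dosing every two weeks (Q2W) to all others.

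**Current gap, completers of the standard schedule.**
- 51 − 1 = 50 weeks after the only scheduled test.
- That is about 50 doses if weekly, or 50 / 2 = 25 if Q2W.

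**Gaps with tests at Visits 4, 8, 12 and 16.**

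| Interval | Weeks | Gap (weeks) |
|---|---|---|
| Visit 1 to 4 | 12 − 1 | 11 |
| Visit 4 to 8 | 25 − 12 | 13 |
| Visit 8 to 12 | 38 − 25 | 13 |
| Visit 12 to 16 | 51 − 38 | 13 |

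The longest gap falls from 50 to 13 weeks.

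**Early exits.** Subjects above 15 eos/hpf leave around week 12 to 13, so their current gap is 12 − 1 = 11 to 13 − 1 = 12 weeks. Under section 3.1.1, subjects at 6 to 15 eos/hpf receive 12 more weeks and may leave around 12 + 12 = week 24. Their gap is now 24 − 1 = 23 weeks. With tests at Visit 4 and at the end of the extension, the longest gap is 24 − 12 = 12 weeks.

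**Dispensing visits.** The row "Dispense Study Drug" in Table 1 is marked at Visits 1–6, 8–10 and 12–14, which is 6 + 3 + 3 = 12 visits. A same-visit test exists at 1 of 12 now, and would exist at 4 of 12 (Visits 1, 4, 8, 12) with the change.

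**Would more tests help?** The Table 1 footnote "Visits can be done via remote research visit" applies to Visits 6, 7, 10, 11, 14 and 15. The other visits up to Visit 16 fall at weeks 1, 3, 8, 12, 13, 25, 26, 38, 39 and 51, with gaps of 2, 5, 4, 1, 12, 1, 12, 1 and 12 weeks. Testing at all of them would lower the longest gap only from 13 to 12 weeks, so the four proposed visits give nearly all the gain available in person.

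**The case against.** The case for leaving the schedule alone has real content.

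- **Risk is already limited.** Highly effective contraception is required, and criterion 21 excludes anyone planning pregnancy. Section 5.1.11 says no published reports link dupilumab with harm in pregnancy. This bears on priority: no harm rate can be claimed. But contraception does not detect its own failure, and the protocol has itself decided that dosing must stop.
- **Contact is frequent.** Adverse events are assessed at every visit from 2 to 17, never more than 5 weeks apart by Table 1. These are real chances to pick up a pregnancy. They are not tests, and something must first raise suspicion.
- **Fifty weeks applies to completers only.** Section 5.6 assumes 64% of 30, or 0.64 × 30 ≈ 19 evaluable subjects, so about 30 − 19 = 11 may leave early. Those leaving at week 12 to 13 have a gap no longer than the one the change accepts. This stands.
- **Section 5.1.10 can be read broadly.** It comes under a heading that covers monitoring as well as screening, and its wording would take in a girl after menarche. Even so, it gives no visit at which she would be tested.
- **An unseen policy may already cover this.** Visits 4, 8, 12 and 16 are endoscopy visits, and section 5.1.6 refers to an institutional sedation policy that is not supplied. If that policy requires a pregnancy test, much of the practical gap is already closed. Still missing would be a link from the result to dispensing, and a test at Visit 12 when the week-38 endoscopy is not done, which section 3.1 allows.
- **The remedy is partial.** Gaps of 13 weeks remain, 8 of 12 dispensing visits still lack a same-visit test, and the Visit 16 test cannot hold back a dose because none is dispensed then. All true.

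**Conclusion.** The concern holds. Followed exactly, the plan leaves the stop rule in section 5.1.11 without a scheduled detection step for 50 weeks in completers and 23 weeks in subjects who leave after the extension. A girl premenarchal at Visit 1 has no scheduled test. It should be changed as a cheap safety improvement; it does not threaten the trial's conclusions.

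The reading of the schedule is firm. How far it matters in practice depends on three things the documents do not give: the content of the sedation policy, the number of subjects able to become pregnant, and any rate of contraceptive failure or harm. No count of affected subjects is therefore offered, and the week figures should be read as intervals between scheduled tests only.

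**What to change.** - **Table 1:** mark the urine test also at Visits 4, 8, 12 and 16.
- **Section 4.1.1:** list the Visit 1 test ahead of the first dose.
- **Sections 4.1.4 and 4.2.4:** list the test, with the result known before drug is dispensed at Visits 4, 8 and 12, and as an end-of-treatment test at Visit 16. Perform the Visit 12 test whether or not the week-38 endoscopy takes place.
- **Section 3.1.1:** add a test at the end of any additional 12 weeks of disease control.
- **Section 5.1.10:** name these visits and require childbearing status to be re-checked at each, so that menarche on study triggers testing.

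Section 4.6.1 repeats Visit 8, so the Visit 8 entry also covers early withdrawal. The contraception requirement and the stop rule stay as they are.

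**Cost.** Up to four urine tests per affected subject, or five with the extension, at visits that Table 1 does not allow to be remote and where research blood is already drawn. No extra visit, staff or invasive procedure is needed. A positive urine result would need confirmation, for which inclusion criterion 6 already accepts serum.
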